### **Inclusion Criteria**

- Be  $\geq 25$  years old
- Acknowledge sex with men in the past five years or identify with a minority sexual orientation
- Identify as a male or transgender person who has sex with men
- Spanish or English speakers/readers
- Is HIV-positive or HIV-negative
- Is HPV vaccinated or unvaccinated

### **Exclusion Criteria**

- Have a primary residence that is not in the Chicago or Houston metro areas
- Have had a DARE in the prior 3 months
- Have unresolved health care provider's diagnosis of anal condyloma, hemorrhoids or anal cancer
- Have plans to move in the following 6 months
- Is unable to give informed consent

### **Recruitment Procedures and Setting**

Chicago and Houston staff will use five strategies:

- 1) Social media advertisements to reach persons not accessing clinics and thus more vulnerable to late presentation of disease (e.g., Growlr, Scruff, Jack'd, and Facebook);
- 2) Face-to-face encounters in clinics serving HIV-positive and HIV-negative persons;
- 3) Communication that markets the study within appointment confirmation emails/texts sent by Crofoot Clinic (Houston only)
- 4) Telephone calls to clinic patients;
- 5) CAB-associated peer leader recruitment of friends;
- 6) Pamphlet and flyer distribution at clinic sites and in businesses (e.g., bars), non-profits, and LGBT events.
- 7) Referral Program

The PAC Referral Program will help direct qualified candidates to the study by incentivizing participants to refer partners, friends and family to be a part of the PAC Study. Specifically:

- 1) Study staff will provide already-consented participants with information about the referral program:
  - a. The referral program is designed to spread the word about PAC Study recruitment to men who have sex with men and transgender persons who have sex with men.
  - b. The referral program and the study are entirely voluntary.
  - c. If study participants want to help recruit, they can pass along up to five coupons to their partners, friends and family.

- 2) Each coupon is stamped with a unique number. Staff members will record which coupon numbers were given to which participants.
- 3) Participants can distribute a digital image or hard copy of the coupons to refer persons to the PAC Study Eligibility Survey in REDCap.
- 4) The referred persons then engage in study activities as anyone else with the exception that they will provide the coupon code to a staff person when attending a consenting session. Study team members will ask ‘how did you hear about us?’ or ‘who can we thank for referring you to the study?’
- 5) The participant who referred the person and provided a coupon to person will receive \$20 for each coupon redeemed up to a maximum of five coupons or a total of \$100. Form of payment, e.g., debit card, gift card or cash app, is up to local site. Sites may decide to pay the referrer after each coupon is received or at regular intervals (e.g., bimonthly).

The study will recruit individuals in each city over 27 months. We will record data on recruitment activities, number of calls and website hits, number who decline, ineligibles, and those not keeping appointments.

Houston. In 2015, 2,084,981 males, aged 25-79 lived in the Houston metropolitan area. If 6.3% of these are MSM, then more than 130,000 MSM live in the metro area. Key recruitment sites are the Crofoot Clinic (i.e., the primary clinic site in Houston), Thomas Street Health Center (TSHC), Legacy Community Health Services (all of which are neighborhood clinics with annual caseloads from 2495 to 5000 MSM), the Montrose Center with multiple projects serving lesbian, gay, bisexual, and transgender people (LGBT), and LGBT businesses and non-profits.

Chicago. In 2015, 3,073,639 males, aged 25-79 lived in the Chicago metropolitan area. If 6.8% of these are MSM, then more than 200,000 MSM live in the metro area. Key recruitment sites are the Chicago Center for HIV Elimination (over 1500 MSM visits in 2014-2015), Connect Health (a sexual health clinic housed in the Infectious Disease department at UChicago, the UChicago HIV prevention and treatment clinic, and two Federally Qualified Health Centers where UChicago providers see patients for HIV treatment and prevention. These sites serve a high proportion of African-American MSM on Chicago’s South Side.

### **Community Advisory Board**

In both Houston and Chicago, we will rely on a 10-member community advisory board (CAB) in each city for overall guidance. Comprised of both HIV-positive and HIV-negative MSM and TSM and agency representatives who serve them, we will partner with the CAB to ensure study materials are culturally competent for middle-aged, older, and racial and ethnic minority MSM and TSM. After training on study objectives, anal cancer, and the pilot study, the CABs will provide guidance on culturally competent recruitment, educational material design, participant follow-up, and results interpretation. The CAB in Houston will convene for an inaugural dinner during the first 6 months with regular meetings thereafter. The CAB in Chicago already exists and is ongoing.

### **Eligibility Procedures**

Interested persons will click on a link in recruitment adds or material (or scan a QR code). Persons may also act on recruitment material with telephone calls to study staff. The link will

take them to a short description of the study in REDCap and then, if interest remains, a short survey will assess eligibility. Once eligibility is determined, the person will be asked to provide name, email, and phone number in REDCap. Once the person has submitted initial contact information, REDCap will notify study staff in the person's city that a prospective participant has been deemed eligible and has provided contact information.

### **Remote Consenting Appointment**

Staff will go into REDCap to get the contact information and then contact the person to set up a virtual appointment for remote consenting through an electronic meeting like WebEx or a smart phone call (see detailed consenting procedure below). For persons without this technology, face-to-face consenting will be an option.

Once consenting is complete, staff will collect other contact information (e.g., address, alternate email and phone numbers). Then, staff will set an appointment for Visit 1. The person will be provided directions and asked not to have receptive anal sex for 24 hours before the scheduled visit and not to douche or do extra cleaning of the anus on the day of the appointment. Persons will also be asked to trim their fingernails short.

To end the Remote Consenting Appointment, participants will complete an online Pre-Exam Survey in either English or Spanish (all public-facing material will be bilingual in Houston and only in English in Chicago) in REDCap. The Pre-Exam survey will collect the person's demographics, co-morbid conditions, and EQ-5D quality of life data, in addition to, knowledge, attitudes, beliefs and behaviors regarding anal cancer, self-examinations, sexuality, and COVID-19.

Once the participant clicks "Submit" for the survey, the Remote Consenting Appointment ends.

[figure not shown]
### **Visit 1**

Before the Visit 1 appointment, reminder emails/texts/calls will be made. Eligibility can be done in person at Visit 1 if preferred for persons calling rather than using the online eligibility survey.

### **Visit 1 Overview**

With identical protocols in Houston and Chicago, persons will receive a short didactic presentation on anal anatomy, practice on pelvic mannequins, and get instructions on doing an ASE or ACE (figure 1). The clinician will then swab the anal canal of each participant, and perform a DARE, without disclosing the results, before leaving participants in private to perform their ASE or ACE. Participants will record their results (as either "normal" or "abnormal") and then get the clinician's DARE result along with any needed referrals; thus, the participant result will be judged against the clinician gold standard. Participants will then complete the post-exam computer-assisted self-interview. At the end of Visit 1, persons will be randomized to a condition of encouraged practice of the ASE (or ACE) or a condition of neither encouragement nor discouragement from practice. Persons will have Visit 2 in 6 months when concordance of self- and companion exam with a clinician DARE will again be assessed. Data collected during these visits will be analyzed to complete the aims.

Figure 1.

## Visit 1 Detail

After assessment for COVID-19 symptoms/signs, participant weight, height, and waist circumference will be measured followed by rooming the participant with 1-3 other persons in the training room. For this group, the study coordinator will provide anal anatomy/disease education and ASE/ACE instruction. The study coordinator will use pelvic mannequin 1 which has a healthy anal canal and mannequin 2 with a 0.6 cm x 1.0 cm tumor on the anal canal wall (Kyoto Kagaku Co., Kyoto, Japan). The study coordinator will demonstrate on the mannequins how to palpate for an anal canal tumor and ask each participant to practice on the mannequins and then identify the mannequin with the tumor. The study coordinator will then review the ASE/ACE pictorial instructions with participants. Key elements of ASE and ACE education are first viewing the perianus region (with a mirror or phone selfie), finding a comfortable position, and making sure the full 360° of the anal canal is palpated.

In brief, the study coordinator will describe a 5-step ASE/ACE: 1) view the perianus, 2) after gloving and adding lube, touch the anal opening and feel for an abnormality, 3) put a finger in to the first knuckle, try to feel 360° around for an abnormality, and then push in to the second knuckle and feel again, 4) pull finger out and then re-insert to perform the procedure again, and 5) (for individuals only) switch hands (or fingers) and repeat to feel 360° of the canal.

The full 360° palpation will be emphasized when practicing on the mannequin by showing the participant that the full circumference is hard to palpate with only one finger. Participants will likely need to switch hands although it may be possible to use the index finger first and then opposable thumb on the same hand to palpate the full anal canal. The manner used by the participant is less important than full palpation of the anal canal. The study coordinator will emphasize that it is not important to distinguish between diseases: any abnormality should be noted. This will end the training session.

After each participant is put in a private exam room, a highly-experienced clinician will collect anal canal exfoliated cells from the participant using a swab. The clinician will follow the Darragh swabbing protocol (e.g., twirling the swab and slowly removing the swab while counting slowly to ten, and applying pressure to the anal canal walls). The clinician will insert the swab into a prelabeled vial with 2 mL of STM, write the date on the vial, and then place the vial in a cooler. Onsite processing of the specimen will occur at the end of each clinic which consists of logging the specimen in REDCap, vortexing for 45 seconds and then aliquoting the liquid into 3 cryovials that are then stored in a -80C freezer. On a monthly basis, the study coordinator will overnight specimens in styrofoam containers to the Medical College of

Wisconsin Tissue Bank laboratory where each specimen will be recorded in a logbook with participant ID# and date. These specimens will be archived and made available for testing of candidate molecular biomarkers. These results may provide further information on the role of ASE, ACE, and DARE in detecting anal abnormalities. The PI will observe the swabbing protocol of the first 5 participants in each clinical site and re-observe on a quarterly basis.

After collection of the anal canal exfoliated cells, the clinician will then perform a DARE without disclosing results to the participant; however, the clinician will describe to the participant the process of the DARE as the DARE is performed (e.g., “I am first looking at the area around your anus to see if there is anything that doesn’t look normal.” And “I am now feeling all the way around your anal canal to make sure I don’t miss any part of it.”). The clinician will be trained to not provide inadvertent cues on DARE results. After completing the DARE, the clinician will then leave the exam room and record the DARE results for both perianus and anal canal according to published guidance. If an abnormality was observed, the clinician will note its location, size in diameter, appearance and color (if perianal) and other notable characteristics. The duration of the anal canal swabbing and DARE will be noted to inform cost-effectiveness analysis.

The first 40 persons in each city will receive a second DARE done by another experienced clinician immediately after the first DARE done by the primary clinician. The clinicians will be kept separate for the two DAREs and not disclose their findings to each other. The second DARE is done to assess the reliability and repeatability of the primary clinician’s DARE.

Once the clinician leaves the exam room, participants will remain and conduct the ASE/ACE. Participants will be trained to stop the procedure if pain is felt. The participant will record on a form the ASE/ACE result: either normal or abnormal. The participant will inform staff that the ASE/ACE is complete. If the participant detects an abnormality, staff will ask if the abnormality was at the perianus and/or anal canal, what it felt like, (i.e., hard or soft) and its size (using varying sizes of circles on paper). Persons will then complete a Post-Exam CASI in the exam room (one member of a couple will do the CASI in another room to give each participant privacy). The couples’ protocol mirrors the individuals’ protocol except that each partner will ask the other for consent before performing the ACE. Prostate and distal rectal palpation will neither be taught nor expected.

The Visit 1 post-exam CASI requires ~20 minutes to complete and asks about ASE/ACE acceptability and self-efficacy, in addition to intentions-to-seek subsequent care, body positioning for the exam, history of anal self-exams, alcohol use, recent sexual behavior (type and frequency), and anogenital hygiene. Questions to support cost effectiveness analysis are included.

While the participant completes the post-exam CASI, the study coordinator will use REDCap to randomize the participant (Arm 1 – practice or Arm 2 – control); if the person is a true negative (the coordinator will possess both participant and clinician results at this point) the study coordinator will check REDCap to determine if this true negative will receive a qualitative interview.

After the post-exam CASI, participants will remain in the exam room (couples will be reunited) and receive DARE results. If the screening result is a true negative (either for an individual, or, for couples, both partners), the study coordinator will provide the results, e.g., “You reported that your anus felt and looked normal and that’s what the clinician said too. So now you know what your anus is like when it’s completely normal. If something changes, you’ll be better able to notice there’s a difference.” If the result is a true positive, false positive or false negative, then the clinician will provide the result.

If there is a finding of an abnormality on DARE, then standard clinical practices will be followed. If needed, clinicians will treat limited external disease, triage other disease, and ask the participant to call if there are any concerns in the following week. If the result is a false positive or false negative, the clinician will request to immediately perform a second DARE for adjudication of the discordant result. All participants with referrals due to abnormal DAREs will be followed to assess care-seeking behavior and outcome.

An exploratory aim of this study is to collect qualitative data at Visit 1 from all persons with a false-positive, false-negative, or true-positive result and a 5% random sample of true-negatives (~65 persons in each city based on pilot data, or ~1 per clinic week over 2 years). Each will be invited to participate in an individual interview of up to 15-minutes conducted by a member of the project team at each clinical site. Interviews will explore anxiety among persons with discordant results and any needed support. Faculty will train staff to use a semi-structured guide for interviews.

### **Randomization**

At the end of Visit 1, all participants will be randomized to one of two conditions: Arm 1 (practice) or Arm 2 (no practice). One-half of participants in each city will be randomly selected and encouraged to practice the ASE/ACE 3 months before Visit 2. Persons randomized to the control arm will neither be encouraged nor discouraged from practicing the ASE/ACE.

#### **Arm 1 - Practice Arm**

Persons in the practice arm will pick a date three months after Visit 1. The study coordinator will record the date and provide participants written ASE/ACE instructions. Participants who report more than minimal pain associated with ASE/ACE at Visit 1, or otherwise have contraindications based on DARE results, will be asked to not to practice if randomized to the practice Arm. However, all persons will be asked to attend Visit 2 to engage in study activities that are not contraindicated at the time of Visit 2. Participants will be reminded that we will schedule a Visit 2 appointment and that we will also contact them in 3 months and periodically to keep in touch to support study retention.

#### **Arm 2 – Non-practice Arm**

Persons in the non-practice arm will be reminded that we will schedule a Visit 2 appointment and that we will also contact them periodically to keep in touch to support study retention. Persons in the non-practice arm will be neither encouraged to practice nor discouraged from practice. If asked about practice, study staff will reply that the participant is not expected to practice since the ASE/ACE is not known at this time to be beneficial. The PAC Palpation Study is trying to determine if it’s beneficial.

After end-of-Visit 1 study staff will provide a \$50 incentive and also tell the participants about the Referral Program for recruitment. Anticipated visit duration is about 75 and 90 minutes for individuals and couples, respectively.

### **Between Visit 1 and Visit 2 study procedures**

#### Arm 1 – Practice.

*If participant had a normal DARE at Visit 1, OR if participant had an abnormal DARE at Visit 1 that required no referral (e.g., a scar or non-prolapsed hemorrhoids),* study staff will make reminder calls (or emails/texts) and follow-up calls for the scheduled practice session. At the follow-up calls, study staff will record the participant's result for the self/companion exam and the level of anxiety and pain, if any, associated with the exam. If the participant reports more than minimal pain and anxiety, they will be asked to return to the clinic for an HCP exam.

If a new abnormality is detected by the participant, i.e., an abnormality not recorded at Visit 1, the study coordinator will request they return to the study clinic site for a clinical examination. While requesting they return to the clinic, staff will record the participant description of the abnormality, and their level of anxiety and pain associated with the ASE/ACE practice. When the participant returns to the clinic, staff will record medical outcomes for each person.

Participants not wanting to return to the clinic will be provided referrals by the health care provider at the clinic. Efforts will be made to contact persons once each week for up to four weeks to encourage a return to the study clinic or completing of the referral elsewhere.

*If participant had an abnormal DARE at Visit 1 that required referral (e.g., condyloma or suspicious lesion),* the person can still participate in practice unless the clinician advises that the ASE/ACE is contraindicated due to the Visit 1 abnormality, or the person reported more than minimal anxiety or pain due to the ASE/ACE at Visit 1. During follow up, staff will ask about referral completion, resolution of the abnormality, and practice ASE/ACE results. If referral has still not been completed, staff will again encourage completion of referral or coming back to an upcoming study clinic for another DARE.

Participant activity and results between Visit 1 and Visit 2 will be documented in REDCap.

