### **Preparation for Visit 2**

Two weeks before the six-month anniversary of Visit 1, staff will contact participant to confirm the Visit 2 appointment time, give instructions for the pre-visit ASE/ACE, and how to report the result. Regardless of prior results, all persons will be asked to return for Visit 2. Persons with a prior contraindication for ASE/ACE will not be asked to complete the Visit 2 ASE/ACE until cleared by a clinician. To reduce loss to follow up, staff will contact participants two days before Visit 2 to encourage attendance.

Participants will complete the Visit 2 pre-exam computer-assisted self-interview before coming to the clinic for Visit 2. The Visit 2 pre-exam CASI will add questions to the Visit 1 pre-exam CASI to assess 1) knowledge retention about how to do an ASE/ACE, 2) use of ASE/ACE between visits, 3) health-seeking behavior if a participant detected an abnormality between

visits,) social desirability bias (to assess response bias related to being compliant about practicing), and social support questions.

After the pre-exam CASI, participants will be asked to do the ASE/ACE at home within 24 hours before the Visit 2 in-clinic visit. ASE/ACE instructions will be provided upon request. The person will then complete an ASE/ACE, record results as either normal or abnormal, and text the result to the study staff as soon as they're done with the anal exam. Persons in the control arm will be asked about performing the ASE/ACE between visits, technique, and frequency to control for potential confounding. Moving the ASE/ACE to a home-based exam will shorten the participant's time in the clinic which, regarding nosocomial infections like coronavirus, supports a safer clinic visit for participants and may encourage more participants to attend the visit.

Participants will complete an online COVID-19 symptoms survey within 24 hours of Visit 2.

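### The recall rule after home practice joins pain and anxiety with *and*, so read literally one marked symptom alone does not bring a participant back to clinic

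*Combined protocol and SAP*

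**What the plan says.** Under Between Visit 1 and Visit 2 study procedures, Arm 1, the protocol separates practice-arm participants by their Visit 1 DARE.

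- **Normal DARE, or abnormal without referral.** At the follow-up call after practice, staff record the result and "the level of anxiety and pain, if any, associated with the exam". The recall rule follows: "If the participant reports more than minimal pain and anxiety, they will be asked to return to the clinic for an HCP exam". A separate rule covers new findings: "If a new abnormality is detected by the participant, i.e., an abnormality not recorded at Visit 1, the study coordinator will request they return".
- **Abnormal DARE with referral.** Practice is allowed unless a clinician advises against it "or the person reported more than minimal anxiety or pain due to the ASE/ACE at Visit 1". Afterwards, "During follow up, staff will ask about referral completion, resolution of the abnormality, and practice ASE/ACE results".

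The section Arm 1 - Practice Arm also decides who should not practise: "Participants who report more than minimal pain associated with ASE/ACE at Visit 1, or otherwise have contraindications based on DARE results".

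Preparation for Visit 2 then says that "participants will be asked to do the ASE/ACE at home within 24 hours before the Visit 2 in-clinic visit", with one exception: "Persons with a prior contraindication for ASE/ACE will not be asked to complete the Visit 2 ASE/ACE until cleared by a clinician".

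**The concern.** Staff ask about two symptoms, but the recall, as written, needs both. A participant with marked pain and no anxiety, or marked anxiety and little pain, meets only half of the condition.

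Either symptom can matter alone. Risks to the Subjects notes that a fissure can make insertion more painful, and Protections against risk lists a fissure among the contraindications for a DARE. The same risk section accepts the anxiety risk because a provider examines the participant at the same visit. Home practice has no such exam, so the recall rule has to supply it.

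At stake is a clinician exam that one symptom should arguably prompt. That exam is also one place where a contraindication to the Visit 2 home exam could be found.

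**Working it through.** The plan gives no figure to reproduce here. The check is a comparison of wording, followed by simple arithmetic on who the rule covers and how long an unrecalled person waits.

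**1. The three symptom rules side by side**

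| Rule | Section | Symptoms needed |
|---|---|---|
| Do not practise at home | Arm 1 - Practice Arm | Pain alone is enough |
| Do not practise at home (referral group) | Between Visit 1 and Visit 2, Arm 1 | Anxiety *or* pain |
| Return for an exam after practice (normal or no-referral group) | Between Visit 1 and Visit 2, Arm 1 | Pain *and* anxiety |

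**2. What the recall rule does under each reading**

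| Above-minimal symptoms after practice | Recall under *and* | Recall under *or* |
|---|---|---|
| Pain only | No | Yes |
| Anxiety only | No | Yes |
| Both | Yes | Yes |

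**3. What else could bring the person back**

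- The new-abnormality rule applies whatever the symptoms, but only if something new is felt.
- Protections against risk prompts a return for a reported abnormal outcome, and treatment or referral for a reported adverse event. It does not say that pain or anxiety counts as either.
- Visit 1 training tells participants to stop if they feel pain, and says that fissure pain may need medical attention. Neither schedules an exam.
- Adverse events are reviewed weekly, which depends on their being captured.
- The monitoring committee watches for severe anxiety in people who think they have felt a malignancy. That is oversight of the trial and does not trigger recall for an individual.

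The remaining gap is one marked symptom, no new abnormality, and no report that staff class as an adverse event or abnormal outcome.

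**4. Wait to the next scheduled clinician exam**

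Practice falls 3 months after Visit 1 and Visit 2 falls at 6 months: 6 − 3 = 3 months.

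**5. People covered by the rule (not people missed)**

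- Practice arm: 800 / 2 = 400 (Sample Size; Randomization).
- Expected abnormal at Visit 1: 0.11 × 800 = 88 (Statistical Analysis, Aim 2). With an even split, 88 / 2 = 44 are in the practice arm.
- Expected in the normal or no-referral group: from 400 − 44 = 356, if every abnormality needs referral, up to 400, if none does.

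These are expected counts, not limits. They are taken before removing people asked not to practise and people who do not practise. The documents give no pain or anxiety rates, so no missed number can be derived.

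**The case against.** The strongest reply is that *and* is only loose drafting. The preceding sentence lists anxiety and pain as two things to record, and the recall rule picks up the same pair. The neighbouring rules can be read as showing that *or* was meant. This may well be right, but it favours the edit: staff in two cities are meant to follow identical protocols, and the sentence they would follow says *and*.

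If *and* was deliberate, there is still no strict contradiction. Deciding who should not practise is a different decision from deciding who should travel back to clinic, and the thresholds may differ. That stands, so inconsistent is the right word. The protocol gives no reason for the higher threshold after practice.

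The fissure example is also narrower than it looks. The clinician inspects the perianal region before the Visit 1 DARE and stops the visit if a fissure is seen, and people with marked Visit 1 pain are asked not to practise. The case therefore needs a new or missed fissure. Practice-arm participants are also contacted periodically, which gives further chances to report a symptom. These points make the gap smaller without closing it.

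A reader might go further and infer that the referral group goes without symptom checks after practice, because neither symptom is among its listed follow-up items. The documents do not establish that. The coordinator forms and scripts appear only as appendix titles and may ask more. The new-abnormality rule and the provisions in Protections against risk can be read as covering both groups. Staff also encourage people with an incomplete referral to complete it or to come back for another DARE.

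**Conclusion.** The point holds for the normal or no-referral group. As written, the rule does not recall someone with one marked symptom, and the other safeguards do not change that trigger. Someone left in the gap waits about 3 months for the next scheduled clinician exam and is asked for a further home exam within a day before it, unless a contraindication is already known.

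This rests on a literal reading of *and*, and on staff not treating the symptom as an adverse event or abnormal outcome. If staff already read the rule as *or*, only the wording is at fault.

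Two inferences would go too far. The 356 to 400 people covered do not measure how many are missed or harmed. Nor does the wording bear on the trial's results: no aim, estimate, sample size or power is affected. This is a minor participant-safety point.

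**What to change.** In the normal or no-referral paragraph of Arm 1 under Between Visit 1 and Visit 2 study procedures, set the recall trigger to *more than minimal pain or anxiety*. The cost is a one-word protocol amendment, a matching check of the call script, and possibly a few more return visits.

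Optionally, state that the same trigger applies at practice follow-up in the referral group. This would be a clarification only, since that group has its own referral follow-up and the call forms may already ask about symptoms.
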